1.1 Background

The diagnosis of an intrauterine fetal demise is in itself a challenging moment. A patient can tell, almost immediately, that something is gravely wrong as the medical team is working to confirm the diagnosis and gather more information. Once diagnosed, a provider's goals are two-fold: first to provide appropriate emotional grievance support to the patient and her family; the second is to deliver the fetus in the safest and most expeditious matter [1, 2].

Current methods applied to the management of a late second and third trimester fetal demise incorporate similar techniques and pharmaceuticals that are utilized for the induction of a term viable pregnancy such as prostaglandin analogues, dilute oxytocin, mechanical cervical dilation with foley balloon, and amniotomy [3]. Despite the need for a safe and swift delivery, there have been few innovations that focus on the delivery of a non-viable fetus or practices that seek to enhance the standard management of these patients over the last several decades [4, 5]. New research involving mifepristone has shown to be a promising addition to third trimester labor augmentation [6].

Mifepristone is a progesterone receptor modulator that is currently recommended by ACOG for use in management of first and second trimester medical abortions [27, 28]. Numerous publications have demonstrated the safety of this competitive progesterone receptor antagonist when utilized to induce labor in the second trimester or for cervical ripening and preparation prior to surgical dilation and evacuation [7-9]. The use of mifepristone, in addition to misoprostol, in second trimester medical abortions has shown that the addition of mifepristone decreases time to completion of abortion by 8 hours compared to misoprostol alone ($p < 0.01$) [26]. Mifepristone has been shown to augment the effects of misoprostol not only in the first and second trimesters, but in the third trimester as well [26].

A recent study in India randomized women at a gestational age of 28 weeks and greater, with diagnosed intrauterine fetal demise, to either receiving 200mg of mifepristone 24 hours prior to initiation of induction with 100mcg of misoprostol every 4 hours or to receiving the misoprostol induction regimen alone. Results showed that induction to delivery in the combination group was 6.54 hours shorter than in the misoprostol group ($p < 0.001$) and that significantly fewer doses of misoprostol were required for delivery completion in the combination group [30].

The delayed dosage intervals of >24 hours between mifepristone and misoprostol in previous publications does not reflect the care implemented at most United States hospitals [6, 13]. At the time of diagnosis of fetal demise, a woman is typically offered and requests same-day admission to the hospital and definitive management via an induction of labor. Utilization of mifepristone at the time of admission and initiation

of induction has not been studied in a prospective randomized trial. This is clinically relevant for the typical and practical management of fetal demise in the late second and third trimester where the standard of care in the United States is to ascertain the diagnosis and then implement management during that same day or admission. The information gained from physical exam and ultrasound are rarely able to identify exactly at what point in time the fetal death had occurred. However, ultrasound is a powerful and specific diagnostic tool, which can assure the veracity of the diagnosis when made. Women are offered induction of labor at the time of diagnosis to minimize their suffering, and mitigate potential complications such as: coagulopathy, sepsis, and hemorrhage [22].

In July of 2015, the CDC released the most updated statistical report on fetal and perinatal mortality. There were 23,595 documented fetal deaths in the year 2013, gestational age 20 weeks and greater. Minority and marginalized women are disproportionately affected; with black women comprising 26% and Hispanic women comprising 20% of the reported cases [34]. Our Bronx population includes these vulnerable populations, who stand to gain the most from evidence based protocols and improvements in the management of fetal demise. The community surrounding our Montefiore Weiler and Wakefield labor and delivery is identified as 45.3% Black and 58.4% Hispanic by US Census data [35]. Safely shortening the length of labor induction can greatly benefit the emotional and medical safety of our patients. A prolonged induction puts a woman at increased risk for: coagulopathy, sepsis, hemorrhage, and complications that require surgical intervention [22]. Mifepristone has a well-tested and known safety profile and has been proven to optimize the effects of misoprostol, which is the standard medication for induction of labor in the setting of fetal demise [6].

1.2 Hypothesis:

The addition of mifepristone, when compared to placebo, to the standard accepted methods of induction of labor will expedite time to delivery of the fetus in women with intra-uterine fetal demise at 20 weeks gestational age and greater.

1.3 Objectives:

1. To compare time to delivery of fetus after administration of mifepristone or placebo at the onset of labor induction.
2. To calculate the duration of induction and hospitalization time among the two groups including time to delivery of placenta, duration of time on labor and delivery, time as an inpatient, and number of nights in the hospital.
3. To determine the number of women, in each arm of the study, who require surgical interventions due to a failed induction or retained products of conception.

4. To determine if administration of mifepristone augments misoprostol, oxytocin and mechanical cervical dilation.
5. To explore the overall incidence of complications and their association with mifepristone use, such as febrile morbidity, infection requiring antibiotics, or transfusion.
6. To assess whether simultaneous start of induction of labor with misoprostol after mifepristone administration versus subsequent administration or delays in the administration of misoprostol after mifepristone administration makes a difference in the time to delivery of the fetus and to assess the optimal lag time between the two medications.

1.4 Expected Outcomes:

It is expected that the addition of mifepristone will allow for more an expeditious delivery of the fetus among women who present with fetal demise greater than 20 weeks gestation age. It is the intention of the researchers that our results will be submitted for internal quality improvement assessment, scientific meeting presentation and peer review publication. We hope to impact our institutional practice as well as regional and national guidelines regarding the management of second and third trimester fetal demise.

II Study Design

2.1 Proposed Protocol:

We propose a double blinded, randomized, placebo-controlled clinical trial at the time of initiation of induction of labor for fetal demise at 20 weeks gestational age or greater.

1. Diagnose fetal demise: confirm absence of fetal heart motion by attending physician as per the institutional standards and protocols.
2. Confirm gestational age at presentation to labor and delivery based on available medical records and/or ultrasonography as per standard practice and institutional protocols.
3. Based on inclusion and exclusion criteria potential participants will be informed about the research, offered the opportunity to contribute, and trained research staff will complete the informed consent process. After documentation of consent and discussion of the research as indicated the participants will be randomized to the intervention or control arm. Both groups will receive emotional and physical support with induction of labor as per practice guidelines and standard of care by Montefiore physicians, faculty and staff irrespective of participation or assignment.

4. Interventional Arm: Ingest 200mg tab of mifepristone orally. This will coincide with or be implemented prior to the initiation of the induction of labor plan as delineated by the attending physician. The timing will be sensitive to the needs of the participant and the labor and delivery room staff.
5. Control Arm: Ingest a placebo tab orally with similar physical properties. This will coincide with or be implemented prior to the initiation of the induction of labor plan as delineated by the attending physician. The timing will be sensitive to the needs of the participant and the labor and delivery room staff.
6. Montefiore protocol for induction of labor:
 - a. 12w0d-23w6d: Misoprostol 400 micrograms vaginally every 3 hours for 5 doses.
 - b. 24w0d-28w6d: Misoprostol 400micrograms vaginally every 6 hours for 5 doses.
 - c. 29w0d and older: Misoprostol 25-50mcg vaginally every 4 hours for 4 doses OR 100mcg vaginally every 12 hours for 4 doses.
 - d. Induction methods and protocols will be at the discretion of the physician team and tailored to the clinical context.
7. Data: Patient data will be collected by the Labor and Delivery staff via electronic medical record or paper record that will be scanned into the electronic medical record. The investigators will use data abstraction tools to collect information such as time of medication administration, medications administered, time of delivery of fetus, duration of admittance to labor and delivery, and postpartum course, or complications from the electronic medical record.

2.2 Definitions:

1. Intrauterine Demise: Absence of fetal heart motion on bedside ultrasound; confirmed by two separate providers and the attending physician.
2. Mifepristone: A 19-nor-steroid derivative of norethindrone that competitively binds to progesterone and glucocorticoid receptors, with antagonist effect. Mifepristone administration is the standard of care when providing medical management for first and second trimester terminations/abortions as per the American Congress of Obstetricians and Gynecologists.
3. Induction of Labor: The use of medications and other techniques to induce contractions and cervical change with the goal of effecting delivery and evacuation of all uterine contents.

2.3 Protocol Amendments:

All amendments to the protocol by the primary research team will be delineated on handouts and distributed at participating Labor and Delivery Units at 8AM the following day. The same information

will be electronically mailed to resident physicians, attending physicians, physician assistants and nurse managers currently staffing the participating Labor and Delivery units.

III Drug Information

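### Objective 6 seeks an optimal mifepristone-to-misoprostol lag, but lag is not randomised, no both-arm or adjusted analysis is planned for it, and 37 women per arm cannot establish an optimum

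*Combined protocol and SAP*

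**What the plan says.** - **The aim.** Section 1.3, Objective 6, asks whether simultaneous or later misoprostol "makes a difference in the time to delivery of the fetus and to assess the optimal lag time between the two medications".
- **How the lag arises.** On taking the tablet, section 2.1 (items 4 and 5) and section 4.1 say the same for both arms: "This will coincide with or be implemented prior to the initiation of the induction of labor plan as delineated by the attending physician". They add: "The timing will be sensitive to the needs of the participant and the labor and delivery room staff". Section V randomises the tablet, mifepristone or placebo, and nothing else.
- **The induction itself.** Section 2.1, item 6, sets misoprostol schedules by gestational-age band, allows two schedules in the oldest band ("29w0d and older: Misoprostol 25-50mcg vaginally every 4 hours for 4 doses OR 100mcg vaginally every 12 hours for 4 doses"), and then adds: "Induction methods and protocols will be at the discretion of the physician team and tailored to the clinical context".
- **The analysis.** Section 7.2 specifies a t-test and a Wilcoxon test for the primary outcome, and descriptive statistics with ANOVA or chi-square for secondary outcomes. It does not mention lag, covariates or an interaction. The only confounder named anywhere is medication acting on CYP3A4, and only if its use differs between arms (section 3.1).
- **The data.** Medication and delivery times (section 2.1, item 7), gestational age, parity and admission cervical exam (section VI) are all collected.
- **The ambition.** Section 1.4 says of the results in general: "We hope to impact our institutional practice as well as regional and national guidelines regarding the management of second and third trimester fetal demise".

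**The concern.** An optimal lag is a causal claim about timing. Women whose misoprostol starts promptly and women whose start is delayed are sorted by clinical plan, personal need and staffing, not by chance. Comparing them within the mifepristone arm therefore mixes any effect of timing with whatever led to the delay. Applied to lag groups as written, section 7.2 gives exactly that comparison, unadjusted. The placebo women also have a tablet-to-misoprostol interval and could help to separate the two, but the plan does not say they will be used.

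Separately, the trial is sized for one two-arm difference. Splitting one arm by lag leaves too few women to say which lag is best. At stake is a reported best lag that reflects chance or who was delayed, from a team that hopes its results will reach guidelines.

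**Working it through.** **1. The plan's own figure.** Section 7.1 gives SD 6 h, difference 4 h, two-sided alpha 0.05 and power 0.80. Normal approximation: n = 2 × (1.96 + 0.84)² × 6² / 4² = 35.3, so 36 per arm. The exact t-test needs 36.3, so 37 per arm, as stated (power 0.81). The same sum for two lag groups asks for 37 per lag group, or 2 × 37 = 74 mifepristone women. There are 37.

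**2. Precision for lag.** The documents give no lag distribution, so the splits are assumptions. With n1 and n2 the early and late women in one arm:

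- Early versus late within mifepristone: SE = 6 × √(1/n1 + 1/n2), 35 df, t = 2.03.
- Early-late difference in drug effect, both arms: SE = 6 × √(2 × (1/n1 + 1/n2)), 70 df, t = 1.99.

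| Split of 37 | Within mifepristone | Difference in drug effect |
|---|---|---|
| 18.5 / 18.5 | SE 1.97, CI ±4.0 h | SE 2.79, CI ±5.6 h |
| 29.6 / 7.4 | SE 2.47, CI ±5.0 h | SE 3.49, CI ±7.0 h |

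If 20% of each arm received no misoprostol (assumed), the even split leaves 14.8 per cell: SE = 6 × √(4/14.8) = 3.12, CI ±6.25 h.

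**3. Power.** Within mifepristone, power for a 4 h early-late difference is 50% (18 v 19) or 39% (28 v 9). For a 4 h difference in drug effect with an even split, it is about 29% (noncentral t, 4/2.79 = 1.43), and the difference detectable with 80% power is 7.9 h. Reaching 80% power for 4 h would take about 142 per arm (4 × 35.3 = 141.3).

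**4. Finding an optimum.** If lag has no effect at all, the best and worst of three equal lag groups among 37 women still differ by 2.9 h on average, and by 4 h or more in 22% of trials. With four groups the figures are 4.1 h and 48%. Conversely, suppose a true U-shape on an assumed 0-12 h range, with delivery 4 h slower at both ends. In 10,000 simulated trials a quadratic fit finds significant curvature in about one trial in five. About 17% of fits have no interior optimum, and in the rest the middle 95% of estimated optima runs from 2.5 to 9.6 h.

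**5. Confounding: hypothetical only.** A factor worth F hours, with prevalence p1 in delayed and p0 in prompt women, shifts the mifepristone-only contrast by F × (p1 − p0). For F = 4 h, 60% v 40% gives 0.8 h and 70% v 30% gives 1.6 h. With no true lag effect, p<0.05 then occurs in about 7% and 13% of 6,000 simulated trials, against a nominal 5%. None of these inputs comes from the documents.

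**6. What a both-arm contrast buys.** It cancels a factor that acts equally, and relates equally to lag, in both arms. Two cases where it does not (assumed, 70% v 30%):

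- Factor worth 4 h on placebo and 2 h on mifepristone: shift (2 − 4) × 0.4 = −0.8 h. Main-effect adjustment leaves this. An arm-by-factor term removes it, with SE about 3.1 h instead of 2.8 h.
- Factor worth 4 h in both arms but tied to lag only on mifepristone: shift 4 × 0.4 = 1.6 h, as large as in the mifepristone-only comparison.

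**The case against.** The best case for the plan is that Objective 6 is the last of six. The hypothesis (1.2) and sample size (7.1) concern only the addition of mifepristone, and the guideline sentence in 1.4 is about the results generally. The objective says it will assess an optimum, which is weaker than claiming to establish one. ANOVA could carry an arm-by-lag term. All of this is fair and limits the weight of the point. It does not supply an analysis: nothing in 7.2 says that such a term, or the placebo women, would be used.

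Confounding is also not demonstrated. Gestational age is the natural candidate because the misoprostol schedules follow it, but physician discretion can override them and nothing links gestational age to lag. That stands, so the illustrative shifts above carry no evidential weight. The precision results do not depend on them.

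The strongest objection is to the remedy. Lag, like receipt of misoprostol, arises after the tablet. Section 3.1 suggests mifepristone may act within hours, so the drug could influence when misoprostol is started. Baseline adjustment would not repair that. This stands and is carried into the fix as a caveat. It also stands that the documents do not identify parity or cervical exam as confounders; they are proposed as recorded baseline characteristics. Nor does the proposed model capture discretionary choice of regimen beyond gestational age.

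**Conclusion.** The point holds for a secondary objective. The lag is not randomised, section 7.2 gives no both-arm or adjusted analysis of it, and the sample cannot establish an optimum. With SD 6 h and 37 per arm, the confidence limits (±4.0 to ±5.0 h within mifepristone, ±5.6 to ±7.0 h for the difference in drug effect) are as wide as or wider than the 4 h effect the whole trial seeks. The splits are assumed, but an even split is the most favourable two-group case.

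A reader might infer three stronger things that the documents do not support:

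- *That lag confounds the primary result.* It does not; drug versus placebo is randomised.
- *That delayed women are known to differ, or that a known bias is present.* The documents leave the reasons for delay open and give no size.
- *That the choice of time zero biases Objective 6.* Objective 1 refers to time after the tablet and Objective 2 to duration of induction. Which clock applies is a separate question of definition and forms no part of this point.

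**What to change.** 1. **Section 1.3.** Replace the optimal-lag clause with an exploratory aim: *explore whether the mifepristone effect varies with lag*. State that lag is not randomised.
2. **Section 7.2.** Analyse Objective 6 in both arms among women given misoprostol, with arm, tablet-to-first-misoprostol lag and arm-by-lag terms, adjusted for gestational age, parity and admission cervical exam. Add an arm-by-gestational-age term as a sensitivity analysis. Report the interaction with its 95% CI and make no claim of an optimum.
3. **Reporting.** Give the lag distribution and the number without misoprostol by arm. State that lag and receipt of misoprostol both arise after randomisation and could be affected by the tablet, so the interaction may still be biased. Where a planned start time is known before randomisation, use planned lag as a sensitivity analysis.

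The primary analysis stays as it is.

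**Cost.** A small protocol amendment for 1.3, wording in 7.2, and one optional case report form field for planned start; the other data are already collected. The interaction will be imprecise. For lags spread evenly over 0-2, 0-4, 0-6 or 0-12 h (assumed), its SE is √2 × 6 / (SD of lag × √37) = 2.4, 1.2, 0.8 or 0.4 h per hour of lag, before covariates. It does not show which lag delivers soonest, and the objective becomes openly exploratory.

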3.1 Study Drug Information

Mifepristone is a 19-nor-steroid derivative of norethindrone that competitively binds to progesterone and glucocorticoid receptors, with antagonist effect. The majority of the drug is absorbed through the gut (70%), it then undergoes demethylation and hydroxylation in P-450 microenzyme systems, namely CYP3A4 [18]. Subsequent monodemethylated, didemethylated and hydroxylated metabolites all maintain significant receptor activity[19]. Mifepristone and its metabolites are bound to alpha 1 acid glycoprotein in serum (AAG); saturation is reached with 100 mg of mifepristone. Peak plasma concentrations are reached within 1-2 hours of ingestion, with rapid distribution, alpha half-life of 1.4 hours, and a long beta half-life, elimination time of 20-30 hours [18]. Dosage regimens of 200 mg or more quickly saturate AAG and with the elaboration of metabolites nonlinear pharmacokinetics results in a large pool of biologically active substrates [19]. The physiologic effects of mifepristone include decidual detachment, necrosis, capillary regression, cervical softening and potentiation of myometrial contractions through the loss of progesterone's inhibitory effects [20]. This profile lends compelling support that mifepristone can confer tissue changes and procedural benefit within hours of administration. Of note, since Mifepristone is mainly metabolized by microenzyme CP3A4, the study will thoroughly review patients' medications/substances that may have the potential to induce/inhibit this enzyme. The safety and toxicity profiles of mifepristone are excellent. The FDA approved regimens for medication abortion in the US includes a dose of 800 mg and does not require any consideration or contraindication for women who are taking cytochrome inducing or inhibiting agents. It is not anticipated that many young, pregnant patients will be on such drugs; however, if a significant difference of patients' intake of such medications is noticed among the study arm compared to the control arm, the analysis of the outcomes will take that into account as a possible confounder, ie. exclude such patients in sub-analysis or control for this as a confounder.

The American Congress of Obstetricians and Gynecologists recommends the use of mifepristone in the management of labor induction for a woman with a first or second trimester fetal demise [27,28]. Clinical trials have proven mifepristone to be effective for cervical ripening for labor induction, shortening operative time in dilation and curettage procedures, decreasing length of completion of induced abortions, and augmenting the effects of misoprostol [26, 30-33]. These effects of mifepristone have not yet been studied in a real-time practical management of second and third trimester fetal demise. There is a dearth of information on how quickly the mifepristone augments the effects of cervidil,

oxytocin, and mechanical cervical dilation – all methods currently known to be safe and effective in augmentation of late second and third trimester fetal demise in medical institutions. The following proposed study will investigate if administration of mifepristone at the time of induction of labor will expedite delivery of a demised fetus. This finding would be a significant improvement to the existing management of fetal demise and a compelling surrogate for the potential morbidity associated with a protracted or failed induction of labor.

3.2 Study Drug Side Effects

The side effects of misoprostol are similar to those one would experience during a labor course: bleeding, abdominal cramping, diarrhea, nausea, vomiting, headache, dizziness, back pain, and tiredness. Any drug can cause an allergic reaction, which could be mild or more serious and can even result in death. Common symptoms of an allergic reaction are rash, itching, skin problems, swelling of the face and throat or trouble breathing.

IV Participant Selection

